 - Partial Response (PR):** A 50% or greater decrease in the product of the bidimensional measurements of the lesion (total tumor size), based on a comparison between the measurements at baseline and after four weeks of treatment with neoadjuvant therapy.
 - No Change (NC):** A 50% decrease in total tumor size cannot be established nor has a 25% increase in the size of the lesion been demonstrated.
 - Progressive Disease (PD):** A 25% or greater increase in the total tumor size of the measurable lesions (calculated on the smallest diameter recorded over time).

V. STUDY ENTRY AND WITHDRAWAL; STUDY PROCEDURES

Required Preregistration Screening Tests and Procedures

The study-specific assessments are detailed in this section and are outlined in the study calendar. Screening assessments must be performed within 28 days prior to enrollment. Any results falling outside of the reference ranges may be repeated at the investigator's discretion. Treatment or visit delays for public holidays or weather conditions do not constitute a protocol violation.

A written, signed informed consent form (ICF) and a Health Insurance Portability and Accountability Act (HIPAA) authorization must be obtained before any study-specific assessments are initiated. A separate consent form for tissue banking of residual tumor specimens would be used. Signed copies of the study consent forms would be given to the subject. and a copy will be filed in the medical record. The original study consent will be kept on file with the study records.

All patients who are consented will be registered in OnCore®, the MCW Cancer Center clinical trial management system. The system is password protected and meets HIPAA requirements.

Registration Procedures

Registration and Monitoring of Patients

1. Patients will be screened for eligibility and registered by a certified research associate/certified research coordinator (CRC/CRA) in the Clinical Trials Office of the Froedtert & the Medical College of Wisconsin Clinical Cancer Center.
2. Patients will be registered in the institutional OnCore® web-based system under the CRA console.

3. Registration of patients and information regarding consenting, eligibility review, on-study status, treatment status and follow-up will be monitored, using the OnCore® calendar system.
4. Serious adverse events (SAEs) and protocol deviations will be reported through the OnCore® reporting system.
5. Questions regarding OnCore systems and data reporting should be reported to OnCore® data management.
6. Questions regarding patient eligibility and registration procedures should be directed to the principal investigator, [name], MS ([contact], [contact], office [contact]).
7. Subject Withdrawal. Given the short nature of the treatment regimen (three to five weeks), and none or few low-grade toxicities are expected, it is not considered likely that a large percentage of patients will withdraw from the study, once endocrine treatment has begun. However, subjects have the right to withdraw from the study at any time. In the rare case that a patient withdraws from the protocol after the initiation of treatment, only the data collected up until the date of withdrawal will be used in analysis.
8. A subject may be withdrawn from the study, if she wishes to decline treatment on the study. Subjects may also be withdrawn if there is a violation of the protocol inclusion and exclusion criteria, as deemed relevant by the treating physician and the principal investigator. As these patients would be withdrawn prior to delivery of study-related treatment, they will then be replaced on the study and not counted toward the total accrual goal of 39 patients. Similarly, patients withdrawing for any other reason prior to delivery of treatment will be replaced on the study and not counted toward the total accrual goal.
9. Patients who withdraw from the study should be treated in accordance with normal standard of care. Follow-up will be per the discretion of the patient's treating physicians, but at a minimum be in accordance with NCCN guidelines.

Pretreatment Period

Screening Assessments

Once the informed consent is signed, proceed with the screening procedures and assessments which must be completed within 28 days of prior to enrollment.

- Physical examination
- Vital signs
- Complete medical history
- Performance status (ECOG, KPS, etc.) (Appendix.2)

- Adverse event assessment
- Current medications
- Blood chemistry assessment, including
 - Complete blood count (CBC) with differential and platelet count
 - Alkaline phosphatase, aspartate aminotransferase/alanine aminotransferase - (ALT/AST)
 - total bilirubin
 - calcium
 - phosphorus,
 - creatinine,
 - potassium,
 - sodium,
 - chloride,
 - bicarbonate,
 - fasting lipid panel (low-density lipoprotein [LDL], total cholesterol, triglycerides) - within the past 12 months.
- Serum or urine pregnancy test for premenopausal women
- Specimen collection for Oncotype Dx and study biomarkers once enrolled.
- Unilateral diagnostic breast mammogram and ultrasound within 60 days of enrollment

Study Procedures during Treatment

Patients must have met eligibility criteria on Day 1 to be treated. The clinic visit can be the same for screening, eligibility assessment and if enrolled, to start treatment with endocrine therapy for week 1. Patient will get treatment for 4 weeks (+/-1 week) before their surgery. No additional clinic follow ups are planned during this period, however can be scheduled per discretion of treating physician.

Surgery

- Diagnostic mammogram and ultrasound are required within 5 days prior to surgery
- Surgical specimen collection for study biomarkers

End of Treatment Visit

The end of treatment visit would be scheduled within 30 days from surgery.

- Physical examination
- Vital signs

- Complete medical history
- Performance status (ECOG, KPS, etc.)
- Current medications
- Adverse event assessment

Long-term/Outcomes Follow-Up Procedures

As standard of care, patients will be followed by oncology provider(s) at least annually after surgery (+/- 3 months). Cancer recurrence outcomes up to five years post-treatment will be collected by chart review annually.

VI. ADVERSE EVENTS: DEFINITIONS AND REPORTING REQUIREMENTS

Adverse Event (AE) and Serious Adverse Events (SAE)

The investigator and team will follow the Medical College of Wisconsin policies related to adverse event reporting. Common Terminology Criteria for Adverse Events (CTCAE) version 5 would be used. This information may be found on the [Human Research Protection Program website](#).

Serious AE (SAE) means any untoward medical occurrence:

- **Death.** Results in death.
- **Life threatening.** Is life threatening (refers to an AE in which the patient was at risk of death at the time of the event; it does not refer to an event which hypothetically might have caused death if it were more severe).
- **Hospitalization.** Requires inpatient hospitalization or prolongation of an existing hospitalization
- **Disability/incapacity.** Results in persistent or significant disability or incapacity. (Disability is defined as a substantial disruption of a person's ability to conduct normal life functions).
- **Medically important event.** This refers to an AE that may not result in death, be immediately life threatening, or require hospitalization, but may be considered serious when, based on appropriate medical judgment, may jeopardize the patient, or require medical or surgical intervention to prevent one of the outcomes listed above.

Unanticipated Problem Involving Risk to Subject or Other (UPIRSO)

The investigator and team will follow the Medical College of Wisconsin policies related to unanticipated problems involving risks to subjects or others. This information may be found on the [Human Research Protection Program website](#).

AE Attribution and Grading

Table 2. Adverse Event Grading

Grades	Description
0	No AE (or within normal limits)
1	Mild; asymptomatic or mild symptoms; clinical or diagnostic observations only; intervention not indicated.
2	Moderate; minimal, local or noninvasive intervention; limiting age-appropriate instrumental ADL*
3	Severe or medically significant but not immediately life-threatening; hospitalization or prolongation of hospitalization indicated; disabling; limiting self-care ADL*
4	Life-threatening consequences; urgent intervention indicated
5	Death related to AE

NCI CTCAE: National Cancer Institute Common Terminology Criteria for Adverse Events; ADL: activities of daily living.

* Instrumental ADLs include preparing meals, shopping, using the telephone, managing money. Self-care ADLs include bathing, dressing, using the toilet, taking medications.

Adverse Event Attribution

Attribution is an assessment of the relationship between the AE and the medical intervention

Table 3. Adverse Event Attribution

Relationship	Attribution	Description
Unrelated to study drug/intervention	Unrelated	The AE is clearly NOT related to the intervention
	Unlikely	The AE is doubtfully related to the intervention
Related to study drug/intervention	Possible	The AE may be related to the intervention
	Probable	The AE is likely related to the intervention
	Definite	The AE is clearly related to the intervention

Relationship Assessment: In-Depth Definitions

For all collected AEs, the clinician who examines and evaluates the subject will determine the adverse event's causality, based on temporal relationship and his/her clinical judgment. The degree of certainty about causality will be graded using the categories below:

Definitely Related: There is clear evidence to suggest a causal relationship, and other possible contributing factors can be ruled out. The clinical event, including an abnormal laboratory test result, occurs in a plausible time relationship to drug administration and cannot be explained by concurrent disease or other drugs or chemicals. The response to withdrawal of the drug (dechallenge) should be clinically plausible. The event must be pharmacologically definitive, with use of a satisfactory rechallenge procedure, if necessary.

Probably Related: There is evidence to suggest a causal relationship, and the influence of other factors is unlikely. The clinical event, including an abnormal laboratory test result, occurs within a reasonable time sequence to administration of the drug, is unlikely to be attributed to concurrent disease or other drugs or chemicals, and follows a clinically reasonable response on withdrawal (dechallenge). Rechallenge information is not required to fulfill this definition.

Possibly Related: There is some evidence to suggest a causal relationship (e.g., the event occurred within a reasonable time after administration of the trial medication). However, the influence of other factors may have contributed to the event (e.g., the subject's clinical condition, other concomitant events). Although an adverse drug event may rate only as "possibly related" soon after discovery, it can be flagged as requiring more information and later be upgraded to "probably related" or "definitely related", as appropriate.

Unlikely: A clinical event, including an abnormal laboratory test result, whose temporal relationship to drug administration makes a causal relationship improbable (e.g., the event did not occur within a reasonable time after administration of the trial medication) and in which other drugs or chemicals or underlying disease provides plausible explanations (e.g., the subject's clinical condition, other concomitant treatments).

Unrelated: The AE is completely independent of study drug administration, and/or evidence exists that the event is definitely related to another etiology. There must be an alternative, definitive etiology documented by the clinician.

Unexpected Adverse Events

Review all unexpected grade 3, and all grade 4, and 5 adverse events, as well as any others requiring expedited reporting as defined in this protocol. (Grades 4 and 5 events

must be reported to the DSMB within five calendar days of study staff's knowledge.)

The drugs used in this study are FDA approved for the use of women with hormone receptive positive breast cancer. The importance of monitoring these drugs used prior to surgery is vital therefore any adverse events that are grade 3, 4, or 5 along with causality of possibly, probable or definitely should be reported to the institutions IRB as per policy.

Expected Adverse Events

The following tables provides the expected adverse events for aromatase inhibitors: Anastrozole, letrozole and exemestane and tamoxifen.

Table 4. Expected Adverse Events for Aromatase inhibitors

Likely	Less Likely	Rare
Fatigue	Hypertension	Heart disease
Joint musculoskeletal pain	Constipation	Chest pain
Loss of bone density over time	Nausea/Vomiting	
	Weight gain	
	Sweating/Hot flashes	
	Mood alteration (depression, anxiety)	
	Hair thinning	
	Headaches	

Table 5. Expected Adverse Events from Tamoxifen

Likely	Less Likely	Rare
Fatigue	Difficulty with sleep	Ischemic cardiovascular event
Hot flashes/Sweating	Constipation	Thromboembolic event
Decrease in libido	Nausea/Vomiting	Uterine cancer
	Weight gain	
	Mood alteration (depression, anxiety)	
	Hair thinning	
	Headache	
	Hypertension	

Patient Assessments

1. As noted, given the short nature of the treatment regimen (three to five weeks), and expected low grades of toxicity, it is considered highly unlikely that a large percentage of patients will experience adverse events (AEs) from the endocrine treatment.

2. All grade 3 and above AEs would be recorded regardless of attributions.
3. Patients would be assessed at beginning and end of treatment with neoadjuvant endocrine therapy as well as at their follow up visit within 30 days after completion of study treatment.
4. Expected side effects are minimal. The most commonly reported symptom is fatigue. Fatigue is characterized by a state of generalized weakness with a pronounced inability to summon sufficient energy to accomplish daily activities.
5. Other less commonly reported side effects are anti-estrogen symptoms, i.e., hot flashes, mood changes and weight changes. Some of the rare but serious side effects, such as ischemic cardiovascular event, thromboembolic event or uterine cancer with tamoxifen are long-term side effects and are not expected to occur during this short course of neoadjuvant treatment. Similarly, decrease in bone density with aromatase inhibitors is a slow and long-term side effect, not expected to be seen during the four-week study period.
6. There are no dose modifications or reductions recommended with endocrine treatment.

VII. STATISTICAL CONSIDERATIONS

Statistical analyses:

Demographic and baseline characteristics, such as age, race, weight, values of all biomarkers pre and post-treatment, response measures will be summarized, using means, standard deviations, medians, ranges for continuous variables, and proportions for categorical variables.

This is an exploratory study to gather information on how frequently protein levels of HER growth factor receptors (HER1-4) are upregulated along with changes in other study biomarkers and correlation with Ki-67 in response to short-term neoadjuvant endocrine in early stage HR+ breast cancer. We hypothesize that expression of one or more HER proteins (HER1-4) will be upregulated in at least 50% of tumors after four weeks of neoadjuvant endocrine therapy and this upregulation will correlate with Ki-67 expressed in more than 10% of cancer cells, as compared to upregulation in 30% or less of tumors without the therapy. The change in Ki-67 expression will be dichotomized, as a categorical variable with $\geq 10\%$ increase coded as high and $< 10\%$ coded as low.

- a) For the primary outcome: An exact binomial one sample test of proportions will be used for to test the hypothesis that proportion of upregulated HER proteins will be at least 50% after therapy versus the null hypothesis that the proportion of upregulated HER proteins is not greater than 30%.
- b) For analyzing - the differences in proportion of upregulated HER proteins between the high difference in Ki-67 and low difference in Ki-67 groups, two sample tests of proportions will be used.
- c) Similarly, appropriate two sample tests will be used to test differences in biomarkers between the high difference in Ki-67 and low difference in Ki-67 groups. We will use the appropriate kind of regression instead of two sample tests, to test differences in biomarkers between the high difference in Ki-67 and low

difference in Ki-67 groups if we need to adjust for covariates.

- d) Additionally, regression analysis will also be done to evaluate the changes in the biomarkers and their association with patient specific covariates, such as age, race and other relevant predictors of interest.

Radiographic responses will be assessed by WHO criteria. Radiographic response rates will be measured as the rate of complete response (CR) or partial response (PR) in patients treated with neoadjuvant endocrine therapy. Complete response is defined as the resolution of tumor on post-treatment imaging as compared with pretreatment imaging, while partial response is defined as 50% reduction in tumor size on post-treatment imaging, as compared with pretreatment imaging. We will estimate the rates of response with 95% confidence intervals. We will use logistic regression (and other generalized linear models as appropriate) to measure association between the response rates and patient specific covariates such as age, race and other relevant predictors of interest.

We will use a family type I error rate of 0.05 significance throughout with Bonferroni adjustments for multiple testing wherever appropriate, so that the overall family type I error rate is maintained.

Sample Size and Power Calculation

To achieve at least 80% power at significance level of 0.05, when testing the one sided one sample hypothesis that the proportion of tumors with HER protein upregulation with neoadjuvant endocrine therapy is at least 50% versus the null hypothesis that the proportion is no larger than 30%, **the minimum number of patients required is 37.**

Early Stopping for Futility

Early stopping for futility and interim analysis in clinical trials are done to ensure safety of the patients and prevent any unnecessary intervention. This is an exploratory study to understand changes in tumor biology with neoadjuvant endocrine treatment. All study biomarkers including changes in HER family of RTKs are being studied to assess responses and development of endocrine resistance. In this study, patients are being treated with endocrine therapy in the neoadjuvant setting for a short duration of time (4 weeks +/- 1 week) without causing any significant delay in their surgery. They will be treated with the same endocrine therapy in the adjuvant setting for at least 5 years which is standard of care. These drugs are routinely used in neoadjuvant setting in patients deemed to be poor surgical candidates or requiring a delay in surgery for variety of reasons and is considered a safe approach with minimal risk to the patients particularly when used for a short duration as done in this study.

The primary objective of this study is to assess changes/upregulation of one or more HER proteins (HER1-4) after neoadjuvant endocrine treatment. Given the exploratory nature and small sample size of this study, we may not see enough upregulation of HER

proteins to meet statistical significance. Up regulation or lack thereof of HER proteins is not a known prognostic factor for patient outcomes at this time and will not impact the safety or clinical management of these patients. Interim analysis and stopping for futility is not indicated in this setting of an exploratory study where the goal is to understand changes in tumor microenvironment to learn more about tumor responses or lack thereof to endocrine treatment. We expect to get important preliminary data from this exploratory study for future follow up clinical trials.

Missing Data management: Observed data will be included in listings, summary tables and statistical analysis, with counts and proportions of missing data, if any. The only likely source of missing data in our study is the absence of some biomarker information due to lack of tissue specimens. As already mentioned, we will attempt to obtain additional biopsy tissue to complete the information, but in case this is not feasible, the evaluation of these biomarkers will be done dropping the missing samples from the analysis. This missed data is likely to be at random and there will be no imputation of missing data.

VIII. PATIENT SAFETY MONITORING AND CONFIDENTIALITY

This study will be reviewed by the Medical College of Wisconsin Cancer Center Data and Safety Monitoring Committee (MCWCC DSMC). A summary of the MCWCC DSMC activities are as follows:

- Review the clinical trial for data integrity and safety
- Review all grade 3 and higher adverse events, as well as any others requiring expedited reporting as defined in this protocol. (Grades 4 and 5 events must be reported to the DSMC within five calendar days of study staff's knowledge.)
- Review all Data and Safety Monitoring reports.
- Submit a summary of any recommendations related to study content.
- Terminate the study if deemed unsafe for patients.

1. A copy of the MCWCC Data and Safety Monitoring Plan and membership roster will be maintained in the study research file and updated as membership changes. The committee will review reports from the study PI twice annually (or more frequently if needed) and provide recommendations on trial continuation, suspension or termination as necessary.
2. Any available DSMC letters will be submitted to the IRB of record as required.
3. Data on patient information and follow-up information will be collected and entered into the password protected OnCore® system. Data will be accessible only by the research team and DSMC.
4. Hard copy forms will be kept in a locked file in offices of the CTO. The forms will be linked to patients by a unique identifier and patient initials in the event that the

identifier is transcribed incorrectly. Access to these forms will be limited to the CRA and PI only as the data collected will be entered in to OnCore®.

IX. QUALITY ASSURANCE

This trial has been determined to be an intermediate risk trial by the MCW Cancer Center Clinical Trials Office Quality Assurance Team. This will be reviewed by the MCW CC CTO Quality Assurance team as follows

- Intermediate risk trials are reviewed every year.
- 20% of subject files will be selected randomly for review (a maximum of 10 subjects at each monitoring time point). Consent/eligibility and objective-based data will be reviewed for those files selected.
- One file will be selected randomly for a comprehensive review at each monitoring time point.
- Regulatory documents (IRB submissions, reportable events, etc.) will be reviewed at each monitoring time point.

References:

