4. After the informed consent is obtained with the patient's signature, the eligibility process begins. If the patient is deemed eligible, then the patient can participate in any study related procedures.
5. Interested patients must meet with a medical oncologist prior to study entry to determine if Oncotype Dx testing is recommended. If recommended and the patient is amenable to the possibility of receiving chemotherapy, there must be adequate biopsy tissue for testing. If adequate tissue is not available for the Oncotype Dx testing, patients may undergo additional biopsies. If a patient plans to decline chemotherapy, regardless of a high Oncotype Dx results, and elects to forgo the test, they will still be eligible for enrollment. If the patient elects to undergo an additional biopsy, but no residual tumor is found, then, the patient is not eligible for the study.
6. The Oncotype Dx assay is obtained initially in order to know which patient would benefit from the addition of adjuvant chemotherapy after her surgery, so that all patients undergo the appropriate standard-of-care postsurgical treatment. Treatment with neoadjuvant endocrine therapy is likely to induce changes within tumor biology and Oncotype Dx assay done after surgery in this setting may not provide reliable results, and thus, will not be performed after surgery.
7. Once enrolled, patients would be treated with the current standard-of-care endocrine therapy. Choice of endocrine therapy (aromatase inhibitors or tamoxifen) would be decided by medical oncologist, following a review of the patient's medical history and menstrual status. The patient would be treated with

endocrine therapy in a neoadjuvant setting for four weeks (+/- 1 week), with dosing continuing until surgery (+/- 2 days).

8. Patient compliance would be monitored by providing a calendar sheet to the patients to log in their daily use of prescribed endocrine therapy (Appendix.1). This calendar sheet will be returned to our clinical trial staff upon completion of the four-week (+/- 1 week) period of neoadjuvant endocrine treatment.

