9. Core biopsy specimens from the initial biopsy at diagnosis would be used for OncotypeDx assay, as well as for study biomarkers assessments. One hematoxylin and eosin slide and up to 15 to 20 unstained charged slides cut at 4 microns thick would be obtained from pathology blocks with residual tumor. These specimens will be reserved for study labs/biomarkers for pre- treatment after the Oncotype has been completed (if applicable). Biomarkers to be assessed pre- and post-treatment are shown in **Table 1**. Details on handling and preparation of tissue specimen and slides for study evaluations are explained in detail below in section **Pathologic Evaluation and Handling of Tissue Specimens**.
10. If adequate tissue is not available for all study biomarkers to be done, additional biopsies will be requested. However, if the patient declines an additional biopsy and enough tissue is available to obtain some but not all study biomarkers, the patient would still qualify and be enrolled to the study.
11. Patients would undergo unilateral diagnostic mammogram and ultrasound within five days prior to surgery to assess radiographic responses to the pretreatment imaging obtained at diagnosis. The CRC/CRN should notify [name] in Radiology prior to surgery. Diagnostic mammogram and the US are to be assessed using WHO criteria for response.
12. Patients would undergo surgery as planned at the end of the four-week (+/- 1 week) period of neoadjuvant endocrine treatment.
13. Surgical specimen would be use for post-treatment assessments. Changes in proliferation marker Ki-67 between pre- and post-treatment tumor specimens would be assessed by our breast pathologists. One hematoxylin and eosin slide and up to 15 to 20 unstained charged slides cut at 4 microns thick would be obtained from pathology blocks with residual tumor. These specimens will be reserved for study labs/biomarkers for post-treatment. Biomarkers to be assessed pre- and post-treatment are shown in **Table 1**. Details on handling and preparation of tissue specimen and slides for study evaluations are explained in detail below in section **Pathologic Evaluation and Handling of Tissue Specimens**.
14. Any remaining tumor tissue would be banked in MCW Tissue Bank according to the MCW Tissue Bank quality control measures. Specimens would be deidentified. A separate consent form would be used for tissue banking. Patients who do not participate in the Tissue Banking are still eligible.

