15. Patients would be treated per standard-of-care guidelines following surgery. The initial Oncotype Dx assay, if done, would be used by the treating medical oncologist to decide if adjuvant chemotherapy is indicated.
16. A follow-up visit would be scheduled within 30 days from surgery. Further follow-up visits would be per the discretion of the patient's treating physicians, who will follow NCCN guidelines.

17. As standard-of-care treatment, patients will be followed by oncology provider(s) at least annually (+/- 3 months). Cancer outcomes up to five years post-treatment will be collected annually (+/- 3 months) by chart review.
18. Given the short course of study treatment (~3-5 weeks) and none-few low-grade toxicities expected, we expect most of our study patients to complete the 4-week study treatment. Patients should be treated for at least 2 weeks with neoadjuvant endocrine therapy to be considered evaluable for the study end points. All dosed patients with at least 2 weeks of neoadjuvant endocrine therapy received would be included in the analyses.
19. All adverse events grade 3 and above, regardless of attribution, will be collected and reviewed at the required timepoints (screening and/or week 1, and end of treatment visit).

Table 1. Biomarkers to be assess pre- and post-treatment with neoadjuvant endocrine therapy

Biomarkers	End Points
Ki-67	Assess change in proliferation with treatment.
HER tyrosine kinase receptor expression	Assess frequency of increased protein levels of HER1-4 and correlation with response to treatment.
ER% / PR%	Assessment of pre- and post-treatment changes and response to treatment.
CK5+/ER- progenitor cells	Assess proportion of CK5+/ER- cancer cells and correlation with response to treatment.
Iron related proteins	Assess changes in protein expression and correlation with responses.
BTK expression	Assess changes in protein expression and correlation with responses.
PD-L1/PD-L2	Assess changes or emergence of protein expression with treatment and correlation with responses.

Pathologic Evaluation and Handling of Tissue Specimens

1. The surgical specimens will be subject to routine pathological analysis. Routine hematoxylin and eosin (H&E) stain will be used for morphological analysis and for the determination of carcinoma diagnosis. The samples will be assessed by our breast pathologists.

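### Item 10 admits patients without requiring tissue for HER1-4 or Ki-67, and the plan does not say how a partly stained HER panel enters the primary test

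*Combined protocol and SAP*

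**What the plan says.** All references are to the combined protocol and SAP.

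- **Treatment Plan, item 10.** A further biopsy is requested when tissue is short. The patient still qualifies "if the patient declines an additional biopsy and enough tissue is available to obtain some but not all study biomarkers". No marker is named as essential, here or in the eligibility criteria.
- **Treatment Plan, item 9.** Where the Oncotype assay is done, it comes before the pre-treatment slides are set aside for the study.
- **Treatment Plan, item 18.** Two weeks of therapy is the only evaluability condition: "All dosed patients with at least 2 weeks of neoadjuvant endocrine therapy received would be included in the analyses".
- **Table 1.** The four receptors share one row: "Assess frequency of increased protein levels of HER1-4 and correlation with response to treatment".
- **Statistical Considerations, Missing Data management.** Lack of tissue is named as the only likely source of missing data. Where more tissue cannot be had, "the evaluation of these biomarkers will be done dropping the missing samples from the analysis". The paragraph adds: "This missed data is likely to be at random and there will be no imputation of missing data". Counts of missing data are to be reported.
- **Statistical Considerations, Statistical analyses and Sample Size.** A tumour counts as a success if any of HER1-4 is upregulated. The test is an exact one-sample binomial, 30% against 50%, one-sided 0.05, with 37 as the minimum number of patients.

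**The concern.** The marker list is long and the tissue limited. My count from Table 1 and the secondary objectives is about 15 stains: Ki-67, HER1-4, ER, PR, CK5, four iron-related proteins, BTK, PD-L1 and PD-L2. The supply is up to 15 to 20 slides. At one stain per slide (an assumption; multiplexing would ease it) the lower figure leaves no slack. With no stated priority, the primary markers may be the ones that go without.

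Two things follow. First, a patient can take up one of the 37 places and yield no primary result. Second, an any-of-four endpoint reacts badly to partial panels: one positive receptor settles the tumour as upregulated, but no partial panel can settle it as not upregulated. The result then depends on a scoring rule that is not written down. At stake is the HER frequency that the Primary Objective says will inform a later randomized trial and, in a close case, the test result.

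**Working it through.** **Inputs.** From Statistical Considerations: p0 = 0.30, p1 = 0.50, one-sided alpha 0.05, exact binomial test, n = 37. Assumed, because the documents give no figure: a share m = 5%, 10% or 20% of patients lacks one receptor at random, and the four receptors are independent and equally likely to be upregulated.

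**1. The plan's own figure.** With the arcsine approximation, h = 2·asin(√0.5) − 2·asin(√0.3) = 0.4115, and n = ((1.645 + 0.842)/0.4115)² = 36.5, so 37 is reproduced. Under the exact test that the plan names, n = 37 needs at least 17 successes, with size 0.0295 and power 0.744. (A cut-off of 16 has size 0.0604.) The baseline with complete panels is therefore 74.4%, not 80%. That is a separate matter and is not counted here.

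**2. Receptor-level rates.** Per-receptor rate r = 1 − (1 − p)^(1/4). Chance that at least one of three measured receptors is up: q = 1 − (1 − r)³. At p = 0.30, r = 0.0853 and q = 0.2347.

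**3. Three rules for a panel lacking one receptor.**

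- *Score on what was stained:* observed rate = p(1 − m) + qm, n = 37. At m = 0.10: 0.270 + 0.0235 = 0.2935.
- *Drop the whole panel:* observed rate = p, n ~ Binomial(37, 1 − m).
- *Keep only if already positive:* observed rate = [p(1 − m) + qm] / [1 − m(1 − q)], n ~ Binomial(37, 1 − m(1 − q)). At m = 0.10: 0.2935/0.9235 = 0.3178.

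The critical value is recomputed at each n and the rejection probability averaged over n. At a true 30%:

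| Rule | Observed rate, m = 5 / 10 / 20% | One-sided type I error |
|---|---|---|
| Score on what was stained | 29.7 / 29.3 / 28.7% | 0.027 / 0.024 / 0.019 |
| Drop the whole panel | 30.0 / 30.0 / 30.0% | 0.037 / 0.035 / 0.035 |
| Keep only if positive | 30.9 / 31.8 / 33.9% | 0.048 / 0.058 / 0.090 |

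Positive correlation between receptors makes the third rule slightly worse (0.049 / 0.061 / 0.097 at latent correlation 0.5) and shrinks the downward bias of the first.

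**4. Scale.** The approximate 95% half-width at 30% and n = 37 is 1.96·√(0.30 × 0.70/37) = 0.148, about 15 points. The largest shift in the table is 3.9 points.

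**5. Power at a true 50% when whole panels are dropped:** about 75%, 72% and 67% at m = 5%, 10% and 20%, against 74.4% with none missing. The figure at 5% is no lower because the exact test moves in steps as n changes.

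**6. Illustration, chosen to lie near the threshold.** Take 33 complete panels with 14 up, and 4 partial panels of which 2 already show a receptor up. Scoring on what was stained gives 16/37, p = 0.060. Dropping partial panels gives 14/33, p = 0.088. Keeping only the positive ones gives 16/35, p = 0.036. One data set gives three p-values on both sides of 0.05.

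**The case against.** The strongest reply is that the plan already deals with this. Item 9 points to Table 1 for the study biomarkers, and Table 1 treats HER as one entry, so obtaining some but not all of them most naturally means whole rows. A missing HER result is then dropped, with counts reported. The partly stained panel is nowhere described. Item 10 also looks like a deliberate inclusive choice, since patients with limited tissue still serve the secondary markers. The study is exploratory and says that significance may not be reached.

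Much of this stands. A wholly missing HER result does have a rule, and Table 1 leans toward treating the panel as a unit. But a lean is not a rule, and item 18 pulls the other way by including every patient with two weeks of drug. Nothing in the reply answers the enrolment gap: the secondary markers may justify admitting such a patient, but she does not help to fill the 37 needed for the primary test.

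Two stronger readings should be resisted.

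- A reader might infer that the plan inflates the HER rate or its type I error. The documents do not support this. No passage describes keeping a partial panel only when it is positive. Scoring on the stained receptors fits item 18 best and errs in the opposite direction. Even the inflating rule stays under 0.05 at 5% missing.
- A reader might take item 5 as a tissue safeguard: "If the patient elects to undergo an additional biopsy, but no residual tumor is found, then, the patient is not eligible for the study". That sentence sits in the Oncotype item and sets no condition on tissue for the study markers.

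**Conclusion.** The point holds and is minor to moderate. The firmer part is the enrolment rule: as written, patients can be enrolled, treated and counted among the 37 without tissue for HER1-4 or Ki-67, and no allowance is made for them. The second part is an ambiguity. At least three scoring rules for a partial panel are compatible with the text, so the direction of any bias is not fixed. Complete-panel analysis is unbiased if tissue is missing at random; the other two rules are biased even then.

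The sizes rest on an assumed 5% to 20% of patients lacking one receptor, and on independent, equally likely receptors. Within that range the shift in the estimate runs from 1.3 points down to 3.9 points up, small beside the sampling error at n = 37. The case for acting is that the rule can be fixed cheaply before any HER result is seen.

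**What to change.** 1. Stain HER1-4 and Ki-67 before the secondary markers, in both the pre- and post-treatment specimens.
2. Limit item 10's allowance to patients whose pre-treatment tissue suffices for HER1-4 and Ki-67. Log how many are not enrolled for this reason, so that selection by tissue remains visible.
3. Define the primary HER test set as at least two weeks of drug (the plan's own minimum) plus a complete paired HER1-4 panel. Exclude every incomplete panel, whatever the measured receptors show. The Ki-67 comparison also needs paired Ki-67.
4. As a sensitivity analysis, report a best- and worst-case bound with undetermined tumours counted all up and then all not up. In the illustration this runs from 16/37 (p = 0.060) to 18/37 (p = 0.013).

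**Cost.** Steps 1, 3 and 4 need protocol and analysis wording and a laboratory stain order. Step 2 needs tissue adequacy for the primary markers to be settled before enrolment. Item 10 already implies such a judgement, but the Screening Assessments list reads "Specimen collection for Oncotype Dx and study biomarkers once enrolled", so the two should be aligned. Expect a few more screen failures and fewer secondary-marker results. If panels are still incomplete, power falls to about 72% at 10% and 67% at 20% missing, against 74.4%; staining the primary markers first should keep that loss small. No extra biopsies or treated patients are needed.

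Separately, the exact-test power at 37 should be restated, and the 37 reconciled with the accrual goal of 39 given under Registration Procedures.
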